10.0 EVALUATION DURING TREATMENT/INTERVENTION

The Table below illustrates the interventions and treatments required at specific time intervals for the study. All evaluations can be performed as frequently as clinically indicated.

Study Requirement	Within 28 days prior to Study Registration	After Study Registration/Before Cisplatin Dose #1	During RT	D1 of Cisplatin Cycle	D8 of Cisplatin Cycle	D15 of Cisplatin Cycle	12+2 weeks after RT	q6 months after RT
Evaluation by Radiation Oncology	X ¹¹		X ¹⁰				X ^{4,11}	X ^{3,4,11}
Evaluation by Medical Oncology ¹¹	X			X ⁸			X ⁴	X ^{3,4}
PET-CT +/- MRI	X	X ¹					X	X ³
Biopsy of Target Tumor	X	X ¹²						
CBC ⁵	X		X	X	X	X	X	X
Mg++, CMP ⁵	X					X		
Pregnancy Test	X							
Peripheral blood sample for immunologic correlate studies, ctDNA, and/or BRCA mutation status		X ²	X ⁹				X	
Cisplatin Administration ⁷			X ⁶	X	X	X		
Toxicity Assessment			X ¹³	X ¹³				

¹ Only if imaging was not done prior to study registration or not performed at MSK

² Obtain only if BRCA 1 or 2 mutation status is unknown at baseline. BRCA 1 or 2 mutation status may also be obtained from the tissue biopsy at baseline. Bloodwork for immune correlates and ctDNA will be obtained at baseline.

³ Recommended but not required.

⁴ May be performed by either radiation oncologist or medical oncologist, but both visits are not required.

⁵ Except at baseline, CBCs will be checked once a week (± 3 days) during cisplatin but prior to administration. Mg2+ and serum chemistries will be obtained on D15 (± 3 days) of every cisplatin cycle.

⁶Radiation will begin following 1-2 weeks of cisplatin. Weekly cisplatin (\pm 3 days) will be continued and delivered concurrently with RT.

⁷ The length of one Cisplatin cycle is 21 days. Cisplatin is administered on D1, D8 and D15 (\pm 3 days) of every cycle. Following the completion of RT, pending no toxicities, but prior to the week 12 post RT evaluable timepoint, patients will continue to receive cisplatin or until POD, based on MD discretion.

⁸ The medical oncologist will evaluate the patient on D1 of each cisplatin cycle. The patient will be assessed for toxicities and will be recorded on a ClinDoc Toxicity form, complete with grade, attribution, start, and stop dates.

⁹ Bloodwork will be obtained during the last week of RT for immune correlates and ctDNA.

¹⁰The radiation oncologist will evaluate the patient weekly during RT at status checks. The patient will be assessed for toxicities and will be recorded on a standard radiation oncology toxicity form, complete with grade, attribution, start, and stop dates.

¹¹Evaluations by both Radiation and Medical oncologists will include: medical history (baseline only), physical exam, ECOG/KPS, review of prior and concurrent medications and vital signs (blood pressure, height, weight, temperature, respiratory rate and heart rate).

¹²If not completed prior to registration

¹³Required weekly during radiation therapy in either the clinic of medical oncology or radiation oncology and then on D1 of each cycle after the completion of radiation therapy.

11.1 TOXICITIES/SIDE EFFECTS

A severe toxicity will be defined as any grade 3 toxicity, attributed to radiation or chemotherapy, which can be observed within 2 months of completion of protocol radiation. Toxicities will be assessed using the CTEP Version 4.0 of the NCI Common Terminology Criteria for Adverse Events (CTCAE version 4.0) at the website:

http://ctep.cancer.gov/protocolDevelopment/electronic_applications/ctc.htm. Patients will be assessed for toxicities until progression or death. Only adverse events that are possibly, probably or definitely related to protocol therapy will be documented on the CTCAE toxicities form and will be collected for data entry. Only hematologic toxicities that are considered Grade ≥ 2 , per CTCAE version 4.0 will be captured for this trial.

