4.1 OVERVIEW OF STUDY DESIGN/INTERVENTION

4.2 Design

This is a single-arm Phase II trial testing the efficacy of concurrent cisplatin and radiation in breast cancer patients with measurable metastatic or locally recurrent tumor, based on HRR status as determined by the MSK-HRR assay. Prior to study enrollment, all patients will require assessment by the radiation oncologist and medical oncologist. Patients will receive a baseline PET-CT +/- MR for evaluation of the tumor to be irradiated and to assess extent of disease systemically. If unavailable within the time specifications of the study, the PET-CT +/- MR will be performed after study registration. Biopsy of the tumor to be irradiated will be performed. Fresh tissue specimens will be sent to the laboratory of [name] for performance of the MSK-HRR Assay. Results from the functional assay will be utilized towards the primary endpoint. Additional unutilized tissue will be sent to the Immune Monitoring Facility Laboratories for TIL analyses to be conducted by [name]. Bloodwork will be sent to the lab of [name] for ctDNA analyses. After the biopsy, patients will undergo simulation for palliative radiation to the tumor site. Following simulation, patient will initiate a 25 mg/m² infusion of cisplatin once a week \pm 3 days. The starting dose will depend on baseline laboratory results within 28 days prior to registration. Following 1-2 weeks of cisplatin, RT will be initiated. Weekly cisplatin (\pm 3 days) will be continued and delivered concurrently with RT. After the completion of RT, weekly cisplatin (\pm 3 days) will be continued until disease progression or until assessment of treatment response at Week 12 post RT (+/- 2 weeks), based on MD discretion. Patients whose HRR status is found to be inevaluable by the MSK assay will not be included in the study and will be replaced by eligible patients.

At Week 12 (12 \pm 2 weeks after RT; with strong recommendation at 12 weeks), repeat imaging with the same imaging methods used for baseline assessment will be performed. Treatment response will be

determined by either PRC or RECIST 1.1.

We estimate accrual will occur at the rate of 15 patients per year. It will take 3.5 years to accrue the total of 54 patients. Patients will be followed up to 24 weeks after completion of RT to determine all study endpoints. Clinical follow-up will continue until death.

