- If serum creatinine is >1.5 mg/dL, delay treatment, provide intravenous hydration and check 12 or 24 hour creatinine clearance, serum creatinine and electrolytes after 24 hours. If the serum

creatinine is ≤ 1.5 mg/dL and creatinine clearance ≥ 60 cc/min, may give full dose of cisplatin. If serum creatinine is 1.6-1.9 and creatinine clearance is between 30-60 cc/min, cisplatin can be given at the discretion of the treating physician. If serum creatinine is >2 OR creatinine clearance is <30 cc/min, hold cisplatin.

- If the patient develops any non-hematologic grade 3-4 toxicity, cisplatin will be held until toxicity is reduced to grade 2 or less. Dose reduction is permitted at the discretion of the treating physician. If a patient experiences grade 2 toxicity (with exception of alopecia) that lasts >2 weeks, cisplatin will be held and dose reduction recommended at discretion of the treating physician. Cisplatin will be discontinued if greater than grade 2 toxicity persists following 2 dose reductions.
- If the patient develops an intercurrent illness (e.g. infection) that, in the opinion of the treating medical oncologist, mandates a delay of cisplatin therapy, the intercurrent illness must be resolved within a time frame such that no more than 2 weekly doses of cisplatin are withheld. If therapy must be withheld for a longer period of time, the patient will be removed from the study.
- Following the completion of RT but prior to the week 12 post RT evaluable timepoint, patients will continue receiving cisplatin based on MD discretion. The dose and schedule of cisplatin after the completion of RT will be at the discretion of the treating MD. If there is a delay of 3 consecutive weeks of treatment, then the patient must discontinue protocol therapy and will be removed from study. Continuation of cisplatin and the dose and schedule of cisplatin after Week 12 post RT assessment will be at the discretion of the treating MD.
- Note: Disruption to the cisplatin treatment schedule for 3 weeks due to unforeseen circumstances, holidays or the patient being on vacation is permitted and will be reviewed on a case-by-case basis.

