11.2 Toxicities of Cisplatin

Nephrotoxicity

A major toxicity of cisplatin is cumulative nephrotoxicity. Tubular necrosis of both proximal and distal renal tubules has been noted in 28-36% of subjects treated with a single dose of 50 mg/m². It is first noted 14 days after a dose and is manifested by elevations in BUN and creatinine, serum uric acid and/or a decrease in creatinine clearance. Renal toxicity becomes more prolonged and severe with repeated courses of the drug. Renal function must return to normal before another dose of cisplatin can be given. Nephrotoxicity can be reduced by IV hydration and mannitol diuresis.

Nausea and Vomiting

Cisplatin causes moderate to severe nausea and vomiting in almost all subjects treated. Nausea and vomiting usually begin within 1 to 4 hours after treatment and lasts up to 24 hours. Various degrees of vomiting, nausea and/or anorexia may persist up to 1 week after the treatment. Delayed nausea and vomiting (beginning 24 hours or more after chemotherapy) has occurred with complete emetic control on the day of cisplatin therapy. The use of prophylactic and continuing antiemetic medication reduces these adverse effects. Subjects should receive prophylactic anti-nausea medications according to ASCO guidelines for highly emetogenic chemotherapy regimens.

Hypomagnesemia

Hypomagnesemia has been reported in subjects treated with cisplatin and is probably related to renal tubular damage. It may become severe enough to cause tetany. Generally, serum electrolytes return to normal levels when cisplatin is discontinued and supplemental electrolytes are administered.

Ototoxicity

Ototoxicity has been observed in up to 31% of subjects treated with a single dose of cisplatin (50 mg/m²) and is manifested by tinnitus and/or hearing loss in the high frequency range (4000-8000 Hz). Decreased ability to hear normal conversational tones may occur occasionally. Ototoxicity can be more severe in children than in adults and more frequent and severe with repeated administration. Hearing loss can be unilateral or bilateral and is usually not reversible.

Myelosuppression

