Myelosuppression occurs in 25-30% of subjects treated with cisplatin. The nadirs in circulating platelets and leukocytes occur between days 18 and 23, with most subjects recovering by day 39. Leukopenia and thrombocytopenia are more pronounced at higher doses (>50 mg/m²) than will be administered in this study. Anemia (a decrease in hemoglobin of 2gm.100 ml) occurs at approximately the same frequency and with the same timing as leukopenia and thrombocytopenia.

Neurotoxicity

Cisplatin neurotoxicity is characterized by peripheral neuropathies, which are sensory in nature but can also include motor difficulties such as reduced deep-tendon reflexes and leg weakness. The symptoms usually occur after prolonged therapy (4-7 months). Cisplatin therapy should be discontinued when serious neuropathy develops (defined in Section 4.2.1). The neuropathy, however, may progress further even after discontinuation of treatment.

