However, we will plan to accrue a total of **62** patients in order to allow for early dropout due to disease progression/death prior to response evaluation, or inability to obtain HRR status from the core biopsy. For the primary analysis, all patients for whom HRR status can be ascertained will be included in the denominator. Patients who progress or die prior to the response evaluation at 12 +/- 2 weeks post-RT will be included as failures. This includes patients with disease progression outside of the irradiated tumor. Patients for whom HRR status cannot be ascertained or who left the study for nondisease related reasons will be replaced.

A secondary analysis of interest is to evaluate the CR rate among the subset of patients who are able to complete the planned study treatment and have a scan at the 12 +/- 2 week post-RT time point. Radiographic complete response (CR) of the irradiated tumor will be counted as a positive response to treatment. Radiographic response less than a CR, progression of the irradiated tumor or appearance of a new lesion within the radiated field will be categorized as a failure to respond to treatment. All other sites of metastatic disease that is outside of the irradiated field will be monitored and counted toward disease progression.

Based on prior experience with the HRR assay, we estimate that approximately 10% of patients will either 1) not have a definitive HRR status, or 2) will not complete the planned study treatment or 3) not have a response assessment at 12-14 week time point. To ensure we have 80% power for both the primary and secondary analyses we have added 8 patients to the sample size for a total of 62. The accrual number has been adjusted to 54 patients.

We expect to accrue 1 to 2 patients per month, or approximately 18 patients per year. Thus, accrual for the trial will be completed in 3.5 years. Based on previous data on the tolerability of cisplatin and radiation extrapolated from head and neck and gynecologic malignancies, we do not anticipate toxicities associated with the study treatment and as such, we have not incorporated an early stopping rule.

Secondary endpoints include overall response rates (CR+PR+stable disease), time to progression and CTCAE v4.0 toxicities. These endpoints will be compared by HRR status using the log-rank test for time-to-event endpoints and Fisher's exact test for binary endpoints.

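### The severe-toxicity window in Section 11.1 closes 2 months after radiation, but protocol cisplatin may run to week 12 ± 2, so a rate reported under that definition would omit events from the last weeks of protocol drug

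*Combined protocol and SAP*

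**What the plan says.** Section 11.1 opens by limiting severe toxicity to grade 3 events that are "attributed to radiation or chemotherapy, which can be observed within 2 months of completion of protocol radiation". The same paragraph adds: "Patients will be assessed for toxicities until progression or death".

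Section 4.2 (Design) says that after radiation weekly cisplatin "will be continued until disease progression or until assessment of treatment response at Week 12 post RT (+/- 2 weeks), based on MD discretion". Section 4.3.1 leaves the post-radiation dose and schedule to the treating physician and looks beyond the assessment as well: "Continuation of cisplatin and the dose and schedule of cisplatin after Week 12 post RT assessment will be at the discretion of the treating MD".

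Section 11.2 describes cisplatin nephrotoxicity as cumulative and says: "Renal toxicity becomes more prolonged and severe with repeated courses of the drug". It puts the first signs of renal injury 14 days after a dose, and says neuropathy usually appears after 4 to 7 months of therapy and may worsen after the drug is stopped.

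Section 14.0 lists the endpoints: "Secondary endpoints include overall response rates (CR+PR+stable disease), time to progression and CTCAE v4.0 toxicities". Binary endpoints are compared by HRR status with Fisher's exact test. It does not use the term severe toxicity and gives no grade threshold or time window for the toxicity endpoint.

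The Section 10.0 table and its footnotes require toxicity assessment weekly during radiation and then on day 1 of each cisplatin cycle. Grade, attribution, and start and stop dates are recorded. The 12-week and 6-monthly columns carry no toxicity mark.

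**The concern.** A definition that includes events attributed to chemotherapy should stay open while protocol chemotherapy is being given. This one can close while weekly cisplatin is still running, at the point of highest cumulative exposure. A grade 3 renal event attributed to cisplatin in week 11 after radiation is, by the rule as written, not a severe toxicity. The same event in week 8 is.

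This is the document's only definition of severe toxicity, and Section 14.0 offers no alternative. If the 11.1 definition supplies the rate for the secondary safety objective, that rate omits late cisplatin events, and omits more of them in patients who stay on the drug longest. Cisplatin stops at progression, so if progression differs by HRR status, the uncounted exposure would also differ between the groups being compared. If instead all CTCAE toxicities are compared, the 11.1 definition has no stated use. The plan does not say which applies.

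**Working it through.** The plan gives no figure to reproduce; this is timeline arithmetic.

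**Inputs**
- Window: 2 months after radiation (11.1). One month = 365.25/12/7 = 4.348 weeks, so 2 months = 8.7 weeks.
- Cisplatin lead-in: 1–2 weeks (4.2).
- Radiation (4.3.2), 4–5 days a week: 15 fractions = 3.0–3.75 weeks; 25 fractions = 5.0–6.25 weeks. For the optional 10–14 Gy boost I assume 2 Gy fractions given after the first 25, so 30–32 fractions = 6.0–8.0 weeks.
- Latest protocol cisplatin: 10, 12 or 14 weeks after radiation (4.2). I assume weekly dosing continues to that point.

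**Step 1. Protocol cisplatin after the window closes** = end of cisplatin − 8.7 weeks.
- Week 10: 10 − 8.7 = 1.3 weeks (about 2 weekly doses)
- Week 12: 12 − 8.7 = 3.3 weeks (about 4 doses)
- Week 14: 14 − 8.7 = 5.3 weeks (about 6 doses)

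At week 12 the whole cisplatin period is lead-in + radiation + 12 = 16 weeks (1 + 3 + 12) to 22 weeks (2 + 8 + 12). The uncovered part is therefore 3.3/22 = 15% to 3.3/16 = 21%. This is the share for a patient who stays on cisplatin to week 12, not an average over patients.

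**Step 2. Delayed effects.** If renal injury first shows 14 days after a dose, injury from doses given later than 8.7 − 2 = 6.7 weeks after radiation first shows outside the window.

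**Step 3. Where the window closes, counted from first cisplatin** = lead-in + radiation + 8.7 weeks. Time on cisplatin to the assessment = lead-in + radiation + 10 to 14 weeks.

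| Schedule | Radiation (weeks) | Window closes | Cisplatin to week 12 ± 2 |
|---|---|---|---|
| Metastatic | 3.0–3.75 | 12.7–14.4 weeks = 2.9–3.3 months | 14.0–19.75 weeks = 3.2–4.5 months |
| Locoregional, no boost | 5.0–6.25 | 14.7–16.9 weeks = 3.4–3.9 months | 16.0–22.25 weeks = 3.7–5.1 months |
| Locoregional, boost | 6.0–8.0 | 15.7–18.7 weeks = 3.6–4.3 months | 17.0–24.0 weeks = 3.9–5.5 months |

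The window closes before month 4 except in boost schedules given at about four fractions a week, and well before month 7 in all of them. Time on cisplatin can reach the 4-to-7-month range, but need not.

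**Step 4. What a 30-day extension does.** 30 days = 4.3 weeks. For cisplatin to week 12, counting would run to 12 + 4.3 = 16.3 weeks after radiation instead of 8.7. From first cisplatin, over all full-duration schedules, it would close between 14.0 + 4.3 = 18.3 weeks (4.2 months) and 24.0 + 4.3 = 28.3 weeks (6.5 months). For a patient who stops cisplatin within 8.7 − 4.3 = 4.4 weeks of radiation, nothing changes.

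**The case against.** The strongest reply is that only a label is windowed. Section 11.1 itself has toxicities assessed until progression or death. Day 1 of every later cycle carries a dated, graded assessment, and Section 17.3 requires serious events to be reported for 30 days after the last treatment. The Section 14.0 endpoint is CTCAE toxicities without a time limit, no analysis or rule names severe toxicity, and there is no early stopping rule for it to drive. All of this stands. A reader might infer that late cisplatin events are lost from the trial, or that the safety result is understated by construction. The documents do not support either. Understatement follows only if the 11.1 definition is the one reported.

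Second, post-radiation cisplatin is discretionary and stops at progression, so the 3.3 weeks applies only to patients who continue to week 12. The documents do not say how many will. This also stands.

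Third, a reader might infer that cisplatin neuropathy, or cumulative toxicity in general, falls wholly outside the window. It does not. The 4 to 7 months refers to duration of therapy, which many patients will not reach, and cumulative toxicity that appears in the first 2.9 to 4.3 months is counted.

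Fourth, a window fixed from the end of radiation suits an objective about concurrent treatment and gives patients similar observation time. A window that follows cisplatin lengthens with time on drug and could unbalance the comparison by HRR status. This is a fair cost of the change, and it is met by reporting both windows.

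One qualification runs the other way. The Section 10.0 table marks no toxicity assessment at 12 weeks or at the 6-monthly visits. Once cisplatin stops, collection rests on the general statement in 11.1.

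**Conclusion.** The mismatch is real. Severe toxicity is defined to include chemotherapy events, but its window closes 8.7 weeks after radiation while protocol cisplatin may run to week 12 ± 2. For patients treated to that assessment, the last 3.3 weeks of protocol cisplatin (range 1.3 to 5.3) and effects first appearing after those doses cannot qualify. The window closes about 2.9 to 4.3 months after first cisplatin, mostly before the period in which the protocol places neuropathy.

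The harm is limited to a severe-toxicity rate computed under 11.1, and to the open question of which definition Section 14.0 uses. The size rests on weekly cisplatin continuing to the assessment; the upper closure figure also rests on 2 Gy boost fractions and 4-day radiation weeks. How many events would be affected cannot be derived from the documents. Importance is minor to moderate, with no effect on the primary endpoint or power.

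**What to change.** In Section 11.1, count severe toxicity from the first cisplatin dose to the later of (a) 2 months after completion of radiation and (b) 30 days after the last protocol cisplatin dose, the period Section 17.3 already uses for serious adverse events. State whether cisplatin given after the week-12 assessment counts as protocol cisplatin for this purpose, since Section 4.3.1 allows it to continue.

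In Section 14.0, state that this definition feeds the toxicity comparison by HRR status, and report the fixed 2-month post-radiation window beside it so that the groups can also be compared over similar observation time. Reconcile the Section 10.0 table with the statement in 11.1 that toxicities are assessed until progression or death.

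The cost is a few sentences and attribution of events over a few more weeks. The reported rate may be slightly higher, and the extended window varies with cisplatin duration. Only what is counted changes; treatment, sample size and primary endpoint stay as they are.

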17.3 Serious Adverse Event (SAE) Reporting

An adverse event is considered serious if it results in ANY of the following outcomes:

- Death
- A life-threatening adverse event
- An adverse event that results in inpatient hospitalization or prolongation of existing hospitalization
- A persistent or significant incapacity or substantial disruption of the ability to conduct normal life functions
- A congenital anomaly/birth defect
- Important Medical Events (IME) that may not result in death, be life threatening, or require hospitalization may be considered serious when, based upon medical judgment, they may jeopardize the patient or participant and may require medical or surgical intervention to prevent one of the outcomes listed in this definition

Note: Hospital admission for a planned procedure/disease treatment is not considered an SAE.

SAE reporting is required as soon as the participant starts investigational treatment/intervention. SAE reporting is required for 30-days after the participant's last investigational treatment/intervention. Any event that occurs after the 30-day period that is unexpected and at least possibly related to protocol treatment must be reported. Please note: Any SAE that occurs prior to the start of investigational treatment/intervention and is related to a screening test or procedure (i.e., a screening biopsy) must be reported.

Please note: Any SAE that occurs prior to the start of investigational treatment/intervention and is related to a screening test or procedure (i.e., a screening biopsy) must be reported.

All SAEs must be submitted in PIMS. If an SAE requires submission to the HRPP office per IRB SOP RR-408 'Reporting of Serious Adverse Events', the SAE report must be submitted within 5 calendar days of the event. All other SAEs must be submitted within 30 calendar days of the event.

The report should contain the following information:

- The date the adverse event occurred
- The adverse event
- The grade of the event
- Relationship of the adverse event to the treatment(s)
- If the AE was expected
- Detailed text that includes the following
 - An explanation of how the AE was handled
 - A description of the participant's condition
 - Indication if the participant remains on the study

- If an amendment will need to be made to the protocol and/or consent form
- If the SAE is an Unanticipated Problem

17.2.1

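### The study dataset omits grade 3 or higher adverse events judged unrelated, so all-cause severe toxicity cannot be tabulated from it and attribution cannot be checked

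*Combined protocol and SAP*

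**What the plan says.** Section 11.1 sets the capture rule: "Only adverse events that are possibly, probably or definitely related to protocol therapy will be documented on the CTCAE toxicities form", and it is these events that are documented "and will be collected for data entry". The filter therefore acts before the database and not at analysis. The same section builds attribution into the definition of the severe event: "A severe toxicity will be defined as any grade 3 toxicity, attributed to radiation or chemotherapy, which can be observed within 2 months" of the end of protocol RT.

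Section 2.0 lists toxicity of the combined treatment as a secondary objective. Section 14.0 makes it an endpoint: "Secondary endpoints include overall response rates (CR+PR+stable disease), time to progression and CTCAE v4.0 toxicities". It adds: "These endpoints will be compared by HRR status". Section 4.2 describes a single-arm trial.

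Three other places bear on the point:

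- **Section 10.0.** The footnotes to the schedule table have toxicities assessed by the medical oncologist "recorded on a ClinDoc Toxicity form, complete with grade, attribution, start, and stop dates". The radiation oncology form carries the same fields.
- **Section 17.3.** "SAE reporting is required as soon as the participant starts investigational treatment/intervention", and it continues for 30 days after the last treatment. Relationship to treatment is an item in the report, not a condition for submitting one. After day 30 only events that are both unexpected and possibly related (or more) must be reported.
- **Section 17.2.2.** An abnormal laboratory value counts as an adverse event on criteria such as discontinuation, need for intervention, clinical importance or grade. None of these is relatedness.

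**The concern.** A treatment-related toxicity rate rests on a clinician's judgement, event by event. With a control arm, all-cause rates could be compared between arms and that judgement would matter less. Here there is no such arm. The remaining safeguard is to hold all severe events with their attribution, so that a reader can see the all-cause rate, the related rate and the distance between them. Section 11.1 removes the events needed for this.

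The removal is one-sided for later review. An event entered as possibly related can be reclassified at analysis. An event judged unrelated was never entered, so reclassifying it would mean going outside the dataset.

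Attribution is also hard in this population. Sections 6.2 and 6.3 admit patients with any prior chemotherapy, including platinum, and with RT completed more than 7 days before entry. Many will have metastatic disease. Several toxicities described in Sections 11.2 and 11.4, such as renal injury, myelosuppression, neuropathy and fracture, could plausibly be put down to earlier treatment or to the cancer.

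Section 14.0 says "we do not anticipate toxicities associated with the study treatment" and for that reason sets no early stopping rule. That sits awkwardly beside the toxicities listed in Section 11, and it adds to the value of a complete record of severe events.

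**Working it through.** No sample size, power or event figure in the documents depends on this point, so there is no stated figure to reproduce. The check sets the capture rules side by side, works out the timing gap, and then asks whether the effect can be sized.

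**Step 1: where a grade 3 or higher event goes.** Section 11.1 words severe toxicity as grade 3; I take grade 3 or higher to be the group of interest.

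| Event | Study dataset (11.1) | SAE reports (17.3) |
|---|---|---|
| Judged possibly related or more | Entered | Also reported if serious and within 30 days of last treatment, or later if unexpected |
| Judged unrelated, not serious | Not entered | Not reported |
| Judged unrelated, serious, within 30 days of last treatment | Not entered | Reported, with relationship recorded |
| Judged unrelated, serious, after 30 days | Not entered | Not required |

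Rows 2 to 4 are missing from the dataset. Row 3 can be found in the SAE reports. Rows 2 and 4 have no required route into either.

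**Step 2: two systems.** SAEs go to PIMS (Section 17.3) and study data to CRDB (Section 16.1). No step reconciles the two, so an event in row 3 can be an SAE and yet be absent from the toxicity endpoint.

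**Step 3: the two windows.** Severe toxicity is counted to 2 months after RT, taken here as 60 days. All-attribution SAE reporting ends 30 days after the last treatment. If cisplatin continues for c days after RT, the uncovered part is max(0, 60 − (c + 30)) days.

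- c = 0 (cisplatin ends with RT): 60 − 30 = 30 days.
- c = 14: 60 − 44 = 16 days.
- c of 30 or more: 0 days.

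Post-RT cisplatin is at the physician's discretion, so c will vary between patients.

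**Step 4: laboratory events.** A laboratory abnormality that leads to a dose interruption is an adverse event under Section 17.2.2. If judged unrelated, it is not entered under Section 11.1. The two sections do not agree on what is collected.

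**Step 5: can the effect be sized?** The documents give neither a true severe-toxicity rate nor a rate of wrong attribution. Every rate below is assumed. Let t be the proportion of the 54 patients with a truly related severe event, and u the share of these judged unrelated. Expected patients lost = 54 × t × u, and recorded rate = t × (1 − u).

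| t | Lost at u = 10% | Lost at u = 50% | Recorded rate |
|---|---|---|---|
| 10% | 54 × 0.10 × 0.10 = 0.5 | 54 × 0.10 × 0.50 = 2.7 | 9% to 5% |
| 20% | 54 × 0.20 × 0.10 = 1.1 | 54 × 0.20 × 0.50 = 5.4 | 18% to 10% |
| 30% | 54 × 0.30 × 0.10 = 1.6 | 54 × 0.30 × 0.50 = 8.1 | 27% to 15% |

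This is only one direction. Let w be the proportion of patients whose only severe event is truly unrelated but is entered as possibly related. The recorded rate is then t × (1 − u) + w, and the net bias is w − t × u. Over the assumed range t × u runs from 0.10 × 0.10 = 1% to 0.30 × 0.50 = 15%. The sign depends on whether w is above or below that, and the documents say nothing about w.

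**The case against.** The strongest defence is that related-only capture matches the endpoint as the plan defines it. The objective is toxicity of the combined treatment, and severe toxicity is defined as an attributed event. An all-cause rate is a different measure, and the related rate would still depend on attribution after the change. That is correct. It does not remove the point, because the filter also discards the events against which the attribution could be tested.

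A reader might infer three stronger things. The documents support none of them.

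- **That severe events labelled unrelated are lost for good.** Section 17.3 requires all SAEs to be submitted up to 30 days after last treatment, with relationship as a reported item. Section 16.1 keeps source documentation and Section 16.2 allows audits. What is true is narrower: the dataset omits these events, and no step is planned to bring them back.
- **That the reported rate must be too low.** Possibly related events are admitted, which is a low threshold. In pretreated patients, some events due to disease or earlier therapy may be counted. The net direction is unknown. The Section 14.0 remark on anticipated toxicity explains the absence of a stopping rule. It does not instruct anyone how to attribute events, and Sections 11.2 and 11.4 tell clinicians what to expect.
- **That a related-only rate would look favourable beside the cervical cancer rates in the rationale for concurrent cisplatin and RT.** The plan commits to no such comparison. Section 3.4 also quotes 51 treatment-related grade 3/4 toxicities from the study of single-agent platinum in 86 patients with metastatic TNBC, and a related-only count is like-for-like with that figure.

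It is also fair to say that the planned comparison by HRR status is less exposed than the absolute rate. Section 5.3 restricts assay results to the study statistician and the primary investigator, so there is little reason to expect attribution to differ by HRR status.

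**Conclusion.** The point holds in a limited form. Under Section 11.1 the study dataset cannot yield an all-cause grade 3 or higher toxicity rate, nor can the attribution behind the treatment-related rate be checked from it. Serious events judged unrelated are in the separate SAE reports up to 30 days after last treatment. Non-serious ones, and serious ones after day 30, have no required route into either system. The post-30-day gap inside the severe-toxicity window is at most about 30 days, and it is nil if cisplatin runs a month or more past RT.

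No bias of stated size or direction is claimed. The figures in Step 5 rest wholly on assumed rates and show only that the question cannot be settled from the data to be collected. The primary endpoint is untouched. This is an inexpensive improvement to a secondary endpoint, worth making because the trial has no control arm.

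**What to change.** Amend Section 11.1 so that every grade 3 or higher adverse event is entered whatever its attribution, using the attribution field already on both toxicity forms. The related-only filter can stay for lower grades if the sponsor wishes.

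In Section 14.0, state that severe toxicity will be reported both all-cause and treatment-related over the 2-month window, and that the counts will be reconciled with the SAE listing before analysis. Reconcile Section 11.1 with Section 17.2.2, so that it is clear whether a laboratory abnormality meeting the adverse event definition is entered when it is judged unrelated.

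The cost is a short amendment and modest extra data entry for unrelated grade 3 or higher events in about 54 patients. No visits, procedures or new form fields are needed.
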